## 7. STATISTICAL METHODS AND DETERMINATION OF SAMPLE SIZE

### 7.1 STATISTICAL DESIGN - MODEL

This is a randomised, double-blind, parallel group, multi-centre trial aiming to show superiority of BI 409306 to placebo as an intervention to prevent relapse in patients with schizophrenia. All patients will be treated for 28 weeks.

The primary objective of the statistical analysis is to determine whether BI 409306 significantly reduces the risk of relapse in comparison to placebo.

The estimand of primary efficacy interest is the test of the hazard ratio of BI 409306 (25 mg q.d. and 50 mg q.d. pooled) vs. placebo using the Wald test for the treatment effect in a stratified Cox proportional hazards model stratified by country, on the full analysis set using the ITT follow-up analysis period. Refer to Sections [7.2](#) and [7.3](#) for more details.

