### 7.2 NULL AND ALTERNATIVE HYPOTHESES

The trial will follow a hierarchical testing strategy. The first hypothesis for the superiority testing of the primary endpoint time to first relapse is (HR = hazard ratio):

$H_0: HR_{BI\ 409306 / placebo} = 1$  vs.  $H_a: HR_{BI\ 409306 / placebo} \neq 1$ , where  $HR_{BI\ 409306}$  is the hazard ratio for the pooled active treatment arms (i.e. BI 409306 50 mg q.d. and BI 409306 25 mg q.d.), over 28 weeks (excluding the withdrawal/taper period)

Superiority will be declared if the hazard ratio between BI 409306 vs. placebo is statistically significantly less than 1 at the two-sided type I error level  $\alpha = 0.05$ .

If the first hypothesis test is determined to be statistically significant, the individual doses will be tested for superiority using Hochberg's step-up test. The method will be to perform the statistical tests and rank the p-values for the individual doses vs. placebo. Let  $p_{(1)} \geq p_{(2)}$  be the two-sided p-values. The corresponding null hypotheses are  $H_{0(1)}$  and  $H_{0(2)}$ .

$H_{0(1)}: HR_{BI\ 409306 / placebo} = 1$  vs.  $H_{a(1)}: HR_{BI\ 409306 / placebo} \neq 1$ , where  $HR_{BI\ 409306}$  is the hazard ratio for the BI 409306 dose with the highest p-value

$H_{0(2)}: HR_{BI\ 409306 / placebo} = 1$  vs.  $H_{a(2)}: HR_{BI\ 409306 / placebo} \neq 1$ , where  $HR_{BI\ 409306}$  is the hazard ratio for the BI 409306 dose with the lowest p-value

Step 1: If  $p_{(1)} \leq 0.05$  then both hypotheses are rejected and both doses are declared statistically significant and testing ends. If  $p_{(1)} > 0.05$ , then  $H_{0(1)}$  is not rejected and the testing proceeds to Step 2.

Step 2: If  $p_{(2)} \leq 0.025$ , then  $H_{0(2)}$  is rejected and this dose is declared statistically significant. If  $p_{(2)} > 0.025$ , then all doses fail.

The remaining alpha after the testing of the primary endpoint (Steps 1 and 2) will be used to test the key secondary endpoint of change from baseline in PANSS positive symptoms. The hypotheses to be tested are:

- H0(3): Mean change from baseline of PANSS positive symptom score after 28 weeks of treatment with BI 409306  
≥ Mean change from baseline of PANSS positive symptom score after 28 weeks of treatment with placebo
- Ha(3): Mean change from baseline of PANSS positive symptom score after 28 weeks of treatment with BI 409306  

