### 7.3.1 Primary endpoint analyses

The primary endpoint is the time to first relapse as defined in [Section 2.1.2](#) over the ITT follow-up period (see definition in [Section 7.3](#)).

The treatment comparison strategy is specified in [Section 7.2](#). The treatment arms will be pooled according to dose, i.e. no distinction will be made between treatment arm randomised to taper or treatment arm randomised to withdrawal.

The equality of the hazard rates will be tested by the Wald test for the treatment effect in a stratified Cox proportional hazards model at the two-sided 5% significance level. The model includes the treatment effect as the only covariate and is stratified by country. Breslow's method for handling ties will be used.

The same stratified Cox proportional hazards model will be used to estimate the hazard ratio of BI 409306 vs. placebo and the asymptotic 95% Wald confidence interval. A hazard ratio of less than one favors BI 409306. The analysis will be implemented using SAS® PROC PHREG. Cox proportional hazard model assumptions will be verified.

In early discontinued patients, if the occurrence of a relapse cannot be determined between the time of discontinuation and last contact, it is assumed that no relapse has occurred. Patients who discontinue study medication will be followed until the end of the trial for the primary endpoint. Patients who are lost-to-follow up will be censored for the primary endpoint at the date of last known patient contact.

A sensitivity analysis will be conducted on the primary endpoint, using the Full Follow-up period (see definition above).

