### 7.7 DETERMINATION OF SAMPLE SIZE

Sample size considerations are given in Table 7.7: 1 based on background placebo relapse rates of 25% and 30% and for hazard reductions for the combined BI 409306 groups vs.

placebo ranging from 45% to 55%, 80% power, a two-sided alpha = 0.05, and 20% dropout after six months.

Table 7.7: 1 Trial sample sizes for selected assumptions of hazard ratios and proportions of placebo failures, with 20% dropout, 80% power, and  $\alpha=0.05$

Placebo failure rate	Hazard reduction a for BI 409306 (both groups combined) to placebo		
	55% a	50% a	45% a
30%	305	385	494
25%	372	470	603

a 55% hazard reduction is the same as a hazard ratio of 0.45; 45% hazard reduction is the same as a hazard ratio of 0.55

The sample size selected was 385 under the assumption that the relapse rate for placebo is 30% and the hazard reduction for BI 409306 is 50%. One hundred twenty-nine (129) patients will be randomised per treatment group in a 1:1:1, making the target total number of randomised patients to be 387.

Seventy-four (74) events (relapses) are needed to be observed to meet the trial objective of 80% power for the comparison of BI 409306 (N=258 for 25 mg q.d. and 50 mg q.d. combined) to placebo (N=129). This will not be an event driven trial, so the trial will end when all randomised patients have reached 6 months exposure, regardless of number of conversions observed.

Calculations were performed using ADDPLAN® 6.1.1 statistical package by [REDACTED].

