4. CHANGES IN THE PLANNED ANALYSIS OF THE STUDY

CTP section 7.5 specifies: All patients will be followed up for relapse [...]. Any patient who has not relapsed will be censored in the analysis of the primary endpoint at the time of last patient contact. In fact, the primary endpoint analysis is the ITT analysis, which is indicated in CTP section 7.3 to include relapses only during the 28-week planned on-treatment period. See Section 6.6 for corrections.

The following additional analyses, which were not mentioned in the CTP, were added:

- Time to Discontinuation was added as a further endpoint.
- Time to Treatment Discontinuation or Relapse was added as a sensitivity analysis to the primary endpoint

Recruitment to this study was stopped early by the Sponsor due to slow enrolment. As a result, statistical power is reduced because of sample size reduction, analyses remain the same as planned, see more details in Section 7.4. A fast-track approach will be taken in order to expedite decision making and for preparation of the planned phase III trials, see more details in Section 9.2.

Details surrounding the planned assessment of the impact of the COVID-19 pandemic on the trial, are specified in section 9.3.

Hazard ratio calculated from the Cox proportional hazard model and a 95% confidence interval around the HR will be provided for primary and secondary endpoint; relative risk reduction and a 95% confidence interval around the RRR will be provided for further endpoints.

Due to the fact that there were cases where the site was not able to enter the data into the iPad in a timely manner and was unable to confirm with the site the actual date the assessment was completed, visit start date as recorded on the CRF will be used as the analysis date. Confirmed that all assessments started on the visit date and therefore it is a reasonable assumption to use the CRF recorded visit date as the analysis date.

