6.6 HANDLING OF MISSING DATA AND OUTLIERS

Assessment of relapse data (primary endpoint):

All patients will be followed up for relapse [...]. Any patient who has not relapsed will be censored in the analysis of the primary endpoint at the time of their planned complete 28-week treatment period. This does not include the T/W period. For AEs that meet the primary endpoint criteria, missing or incomplete AE dates are imputed according to BI standards.

The sensitivity analysis will use the Full Follow-up period to demonstrate the robustness of the results of the main analysis. See revised CTP Section 7.3

PANSS positive symptoms (key secondary analysis)

Change from baseline in PANSS positive symptoms will be evaluated using Mixed effect Model for Repeated Measures (MMRM) approach. This approach allows for missing data, assuming they are missing at random. All patients can be included in the model and missed visits will not be imputed. If a PANSS item is missing, the missing score on that individual PANSS item will not be imputed; if individual PANSS item is missing within a PANSS subscale, this subscale cannot be included in the calculation of the overall PANSS total score. Therefore, patients with missing individual PANSS items will also have a missing PANSS total score at that visit. However, subscale scores will be used for analysis if none of the individual items are missing.

Relative Risk Reduction (RRR)

Per revised CTP Section 7.5.:

All patients in the FAS will be included [...] *regardless of drop-out.*

For

AE dates

Missing or incomplete AE dates are imputed according to BI standards (see "Handling of missing and incomplete AE dates") (3).

PK data

Missing data and outliers of PK data are handled according to Reference (2) and as described in Section 10 of the revised CTP.

In December 2019, during the conduct of the trial, a Visit 8 eCRF page was added to capture
the date and time of the last dose of BI drug intake before the PK sampling performed at Visit
8. For patients who had completed the trial at that time, or patients for whom the visit 8 date
had passed, the data will be used to inform the date and time of the last BI drug
intake.
Sensitivity analysis: the date and time of the last dose of BI drug intake at Visit 8 collected in
the eCRF will be compared to the information recorded in This will be done for

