6.7 BASELINE, TIME WINDOWS AND CALCULATED VISITS

patients for whom both sources of information are available (eCRF and

For all efficacy endpoints, "baseline" is defined as the assessments done at Visit 2, prior to administration of first dose. If this value is not available, the latest measurement prior to treatment administration will be used.

For demographics, medical history, concomitant antipsychotic medication, AEs, concomitant therapies, vital signs and C-SSRS, Visit 1 (screening) will be considered as "baseline". If this value is not available, the earliest value prior to treatment administration will be used.

Visit will be labelled according to the flow chart in the protocol: Visit 1 (for screening), Visit 2 (randomization and start of treatment), Visits 3-19, End of Treatment (EOT), Follow Up (FU) (28 days after Visit 16 for completed patients; 28 days after EOT for early discontinued patients). Planned and actual test days will be calculated relative to the beginning of study as indicated in the following table.

Table 6.7: 1 Visit calculation relative to study start

Visit	Relative to study start			
	Planned test day (every 14 days)	Actual test day		
2	1	1		

TSAP for BI Trial No: 1289-0049 Page 20 of 35

Proprietary confidential information © 2021 Boehringer Ingelheim International GmbH or one or more of its affiliated companies

Visit	Relative to study start			
	Planned test day (every 14 days)	Actual test day		
3	15	Visit 3 date – first dose date +1		
4	29	Visit 4 date – first dose date +1 Visit 5 date – first dose date +1		
5	43			
Etc				
16	197	Visit 16 date – first dose date +1		
T/W 17	Visit 16 + 2 days	T/W 17 date – first dose date + 1		
T/W 18	Visit 16 + 4 days	T/W 18 date – first dose date + 1		
EOT (T/W 19)	Visit 16 + 7 days	EOT (T/W 19 date) – first dose date + 1		
FU	Visit 16 + 28 days	FU date – first dose date + 1		

All time to event analyses will use the visit start date as recorded on the CRF as the analysis date.

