- Patients who chose Early Discontinuation Option 5, i.e. withdrew consent per CTP (for ITT and Full FU analysis): Events (relapses) are counted in the time to event analysis whenever they occur between the first dose of randomized treatment and the patient's date of consent withdrawal.
 - Patients with event counted: <date of event> <date of first drug administration> +1
 - Patients without event counted: <date of consent withdrawal> <date of first drug administration >+1 day
- Patients who are Lost-to-Follow-up (for ITT analysis): Events (relapses) are counted in the time to event analysis whenever they occur between the first dose of randomized treatment and the last at-risk date.

- Patients with event counted: <date of event> <date of first drug administration> +1 day
- Patients without event counted: <date of last at-risk> <date of first drug administration >+1 day

*Please note: Patients who are LTFU during the study (regardless of initial Early Discontinuation choice), but were successfully found towards the end of study via a vital status call, will be included in the Full-FU analysis period by replacing as follows:

• Patients without event counted: <date of vital status/date of EOS> – <date of first drug administration >+1 day

The following SAS code will be used:

```
proc phreg data= primary;
   CLASS &trt.(ref="Placebo") / order=internal;
   model aval*cnsr(1) = &trt./ties=breslow;
   strata countrdc;
   hazardratio 'HR' &trt. /diff=ref cl=both;
run;
```

Subgroup analyses will be performed on the subgroups specified in Section 6.4. Definition of Japanese patients is provided in Section 9.1. The same model as described above for the primary efficacy analysis, will be used for these analyses.

The following SAS code will be used for survival plot:

```
proc lifetest data=primary method=km plots=survival(failure test
atrisk);
time aval*cnsr(1);
id usubjid;
strata &trt. /test=logrank;
run;
```

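### The primary Cox model leaves out baseline PANSS; adding it is a low-cost gain of about 0 to 5 power points, and the treatment-only test is valid without it

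*Protocol*

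**What the plan says.** Protocol 7.3.1 specifies a country-stratified Cox model with a two-sided 5% Wald test: "The model includes the treatment effect as the only covariate and is stratified by country". The synopsis agrees, and Protocol 7.1 writes the same model into its estimand statement, "using the Wald test for the treatment effect in a stratified Cox proportional hazards model stratified by country". The PHREG code in SAP 7.4.1 has a single term, "model aval*cnsr(1) = &trt./ties=breslow", with country on the strata statement.

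SAP 7.4.2 lists two sensitivity analyses. One moves to the treated set and the full follow-up period; the other counts treatment discontinuation as an event. Neither adds a baseline covariate.

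The Flow Chart schedules PANSS at Visits 1 and 2. SAP 6.7 takes the Visit 2 pre-dose value as the efficacy baseline and adds a fallback: "If this value is not available, the latest measurement prior to treatment administration will be used". SAP 6.6 says that "patients with missing individual PANSS items will also have a missing PANSS total score at that visit". The key secondary MMRM already adjusts for the baseline of its own response, the PANSS positive score.

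SAP section 4 records that recruitment stopped early: "statistical power is reduced because of sample size reduction, analyses remain the same as planned".

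**The concern.** In a Cox model, omitting a covariate that predicts the event does not bias the test under the null, but it shrinks the estimated treatment effect: the hazard ratio moves toward 1. Including the covariate restores the estimate without reducing its standard error, so the gain comes from the estimate.

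Baseline PANSS is an obvious candidate. It is scheduled before dosing for everyone, and the second relapse criterion in Protocol 2.1.2 is built on PANSS change from baseline. The plan concedes that power has been lost. Adjustment needs no new patients or data, so the question is how much power it could return and at what cost.

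**Working it through.** **Inputs from the documents.** Placebo relapse 30%, hazard ratio 0.5, 80% power, two-sided alpha 0.05, 20% dropout, 258 pooled active vs 129 placebo, 74 events (Protocol 7.7); 28-week ITT follow-up (Protocol 7.3); country strata (Protocol 7.3.1).

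**Reproducing the plan's figures.**
- Events (Schoenfeld): (1.960 + 0.842)² / [(1/3)(2/3)(ln 0.5)²] = 7.849 / (0.2222 × 0.4805) = 73.5, rounded up to 74. This is the plan's figure.
- Sample size, with exponential relapse and competing exponential dropout: the event probability is 0.271 on placebo and 0.147 on active, with weighted mean (0.271 + 2 × 0.147)/3 = 0.188. Then 73.5/0.188 ≈ 391, against the stated 385 (1.5% apart).

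**Models compared.** Within country: hazard ∝ exp(β·treatment), against hazard ∝ exp(β·treatment + γ·z), where z is standardised baseline PANSS and exp(γ) is the relapse hazard ratio per SD.

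**Assumptions not in the documents.** exp(γ) = 1.0, 1.25, 1.5 or 2.0; z standard normal; the six countries of SAP 5.4.1 with shares 40/20/10/10/10/10%; N=258 as an illustrative one-third cut. The conditional treatment hazard ratio is 0.5. There were 40,000 simulated trials per setting, with both models fitted to the same trials; the Monte Carlo SE of the power difference is 0.05 to 0.17 points. Mean events at N=387 were 73 to 75.

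| HR per SD | N=387: unadjusted → adjusted | Change (points) | N=258: unadjusted → adjusted | Change (points) |
|---|---|---|---|---|
| 1.0 | 82.8 → 82.8% | -0.1 | 66.5 → 66.4% | -0.1 |
| 1.25 | 82.7 → 83.1% | +0.4 | 65.8 → 66.2% | +0.4 |
| 1.5 | 82.0 → 83.3% | +1.3 | 65.0 → 66.4% | +1.4 |
| 2.0 | 79.1 → 83.3% | +4.2 | 62.0 → 66.6% | +4.7 |

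Changes were taken before rounding. For one dose against placebo (129 per arm, tested at 0.05) they are 0.0, +0.5, +1.6 and +5.2 points.

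**Mechanism, at 2.0 per SD and N=387.** The median hazard ratio is 0.521 unadjusted and 0.498 adjusted; the mean SE is 0.2347 and 0.2371. By hand, |ln 0.521|/0.2347 - 1.96 = 0.82, giving power of about 79%, and |ln 0.498|/0.2371 - 1.96 = 0.98, giving about 84%. The SE is slightly larger after adjustment; the estimate does the work.

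**Type I error.** 4.7 to 5.0% for both models.

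**Number of strata.** Protocol 3.3 plans 4 countries. A separate simulation with 4 equally likely strata (6,000 runs per setting) gave -0.1, +1.8 and +4.4 points at 1.0, 1.5 and 2.0 per SD, so the stratum layout matters little.

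**Non-linear effects fitted with one linear term (N=387).** Hazard doubled above the median: +0.7. U-shaped: -0.1.

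**Missing baselines (5% assumed, 1.25 per SD, 20,000 runs).** Treatment-only 82.7%; adjusted with those patients dropped 80.9%; adjusted with mean imputation 82.8%. Dropping patients costs more than a weak covariate returns.

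**Scale.** The assumed cut from 387 to 258 alone costs 82.8 - 66.5 ≈ 16 points.

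**The case against.** The strongest reply is that nothing here is wrong. The synopsis, both protocol sections, the SAP text and the code agree; a treatment-only model is a legitimate choice; and the 74 events are the matching unadjusted number. That is correct, and it is why this is an improvement and not an error.

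The size of the gain is also open to challenge, and much of that challenge stands:

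- **Prognostic strength is unknown.** A hazard ratio of 2.0 per SD means a fourfold hazard between -1 and +1 SD. Patients enter in a stable phase with CGI-S at most 4, PANSS total at most 80 and four key items at most 4 (Protocol 3.3.2). This narrows the spread and makes the lower part of the range more plausible.
- **The link to relapse may not be monotone.** The PANSS-total route needs a 25% rise: 20 points from a baseline of 80, but 11 whole points from 41. High baseline items, by contrast, make the item route easier. The U-shaped run shows that the gain can vanish, at a cost of about 0.1 point.
- **The top of the range is not the planned pooled test at full size.** There the largest gain over the values examined is +4.2. The +5.2 is a single-dose test at 0.05, whereas Protocol 7.2 gates the dose tests behind the pooled test and uses 0.025 at Hochberg's second step.
- **Missing baselines should be rare.** Visit 1 PANSS is an entry criterion and SAP 6.7 has a fallback, so 5% is illustrative only.
- **It is late.** The change would alter the primary model after recruitment stopped, make the target a conditional hazard ratio and add a proportional-hazards assumption for PANSS. It is defensible only before unblinding.

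SAP 6.4, which SAP 7.4.1 cites for subgroups, is not in the public text, so baseline PANSS may appear there as a subgroup factor. That would not put it in the primary model.

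**Conclusion.** The point holds as a cheap, optional efficiency gain. The primary test is valid as written and controls type I error. Adding baseline PANSS changes power by about 0 to 5 points for assumed relapse hazard ratios of 1.0 to 2.0 per SD, with 0 to 2 points the more plausible part. The size rests on the assumed prognostic strength, an approximately log-linear effect and, for the reduced trial, an assumed N. The largest loss simulated with complete baselines was about 0.1 point. The gain offsets only a small part of what early stopping cost, but it asks little in return.

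**What to change.** Before unblinding, add baseline PANSS total as one continuous covariate to the country-stratified Cox model, for both the pooled and the dose-level tests. Use the SAP 6.7 baseline: Visit 2 pre-dose, otherwise the latest pre-treatment value. Where neither yields a total, impute the overall baseline mean, so that no FAS patient leaves the primary test. Report the treatment-only model as supportive.

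Update the model wording in the synopsis and Protocol 7.1 and 7.3.1, and the code in SAP 7.4.1. State that the hazard ratio is conditional on baseline PANSS and extend the planned check of model assumptions to the new term. Say whether the change carries over to the analyses that borrow the primary model: the subgroups in SAP 7.4.1, the discontinuation-or-relapse analysis in SAP 7.4.2 and time to antipsychotic change in SAP 7.5.2.

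The cost is one term in the model statement, one missing-value rule and the matching text. If the sponsor prefers not to change the primary model this late, it should record why; a pre-specified adjusted supportive analysis would then show the conditional estimate but add no power to the confirmatory test.

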## 6.2.2 Treatment period(s)

Eligible patients will be trained and set-up with the smartphone medication adherence monitoring Platform at Visit 2 prior to taking their first dose of study drug. Please refer to the manual in the ISF.

Study medication will be allocated via IRT and dispensed at visits specified in the [Flow Chart](#). Patients will be assigned a new medication number(s) at each of these visits. The first dose of study drug will be administered at the site after all baseline assessments have been completed and trial eligibility confirmed at Visit 2.

See Sections [5.3.2](#) and Section [10.3](#) for the sampling methods and time schedule for PK blood sampling.

Phone Visits are to be conducted at the time points specified in the [Flow Chart](#) to assess the overall status of the patient, assess suicidality, check compliance, and to collect new AE and concomitant medication information. If symptom worsening is suspected, an unscheduled in-clinic visit should be scheduled to further assess the patient for relapse. During the unscheduled visit, information should be gathered to determine whether any criteria for relapse have been met. PANSS and CGI-S should be assessed, as well as any other assessments necessary to assess the patient's condition, in the judgment of the investigator.

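### The primary Cox model is fixed to Breslow's tie approximation although some relapses will tie on visit dates; Efron's method would remove a very small pull of the hazard ratio towards 1

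*Protocol*

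**What the plan says.** Protocol section 7.3.1 prescribes a Cox model for time to first relapse: "The model includes the treatment effect as the only covariate and is stratified by country". For ties it says "Breslow's method for handling ties will be used". The PROC PHREG code in SAP section 7.4.1 carries this through as "model aval*cnsr(1) = &trt./ties=breslow".

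The sensitivity analyses in SAP section 7.4.2 change the subject set and follow-up period, or add treatment discontinuation as an event. None changes the tie method. Time to change in antipsychotic medication (SAP section 7.5.2) is analysed in the same way as the primary endpoint.

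On event dating, SAP section 6.7 states: "All time to event analyses will use the visit start date as recorded on the CRF as the analysis date". SAP section 4 gives the reason, namely that "there were cases where the site was not able to enter the data into the iPad in a timely manner". The protocol flow chart schedules PANSS and CGI-S every 28 days and C-SSRS every 14 days, with windows of ±3 days at Visits 3 to 16.

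**The concern.** When several relapses share a study day within a country, Breslow's likelihood leaves all of them in the risk set for each of the tied failures. If placebo patients fail faster, this overstates the number of placebo failures expected at that time. The observed placebo excess then looks smaller, and the log hazard ratio shrinks towards 0.

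The PANSS/CGI-S and C-SSRS criteria can be met only at a contact, so ties are to be expected here more than in a trial whose events are all dated continuously. The documents give no reason for choosing Breslow. At stake is a small, avoidable attenuation of the primary hazard ratio, in a trial that SAP section 4 already describes as having lost power through early closure of recruitment.

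**Working it through.** **1. The plan's own figure.** Protocol section 7.7 uses HR 0.50, two-sided α 0.05, 80% power and 2:1 allocation (258 v 129). Schoenfeld's formula gives

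events = (1.960 + 0.842)² / [(1/3)(2/3)(ln 0.5)²] = 7.849 / 0.1068 = 73.5, i.e. 74.

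This reproduces the plan. With 30% placebo relapse and 20% dropout, both exponential, N = 391, within 3% of the stated 385. No tie method enters this calculation.

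**2. The two likelihoods.** At a time with d tied events, let S_R be the sum of exp(βz) over the risk set and S_D the same sum over the tied events. The denominators are

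- Breslow: S_R^d
- Efron: the product over l = 0, …, d−1 of [S_R − (l/d) S_D]

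They are identical when d = 1, so only ties within a country stratum matter.

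**3. Simulation at the planning assumptions.** Inputs from the protocol: N = 387, 2:1, placebo relapse 30%, HR 0.50, 20% dropout, 28 weeks; this gives about 73 events. Six country strata follow the list in SAP section 5.4.1. Assumed, not in the documents: country shares of 50/10/10/15/7.5/7.5%, constant hazards and uniform whole-day scatter of visits. There were 2,000 trials per pattern; HRs are geometric means.

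| Event dates | HR Breslow | HR Efron | HR untied | Power Breslow | Power Efron | Verdict at 0.05 differs |
|---|---|---|---|---|---|---|
| Exactly on 28-day visits | 0.509 | 0.503 | 0.503 | 80.6% | 81.5% | 0.9% |
| Exactly on 14-day contacts | 0.506 | 0.503 | 0.503 | 81.1% | 81.5% | 0.5% |
| 28-day visits ±3 days | 0.496 | 0.495 | 0.495 | 83.0% | 83.1% | 0.05% |
| 14-day contacts ±3 days | 0.501 | 0.501 | 0.501 | 82.6% | 82.6% | 0.1% |

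Compare within a row; differences between rows include Monte Carlo error.

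**4. Size against the sampling error.** With 74 events at 2:1, SE(log HR) = 1/√(74 × 2/9) = 0.247. In the first row, ln(0.509/0.503) = 0.012, about 5% of one SE. In the third, ln(0.496/0.495) = 0.002, about 1% of one SE.

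**5. Repeat runs.** A run of 6,000 trials per pattern gave 0.506 v 0.499 on exact 28-day visits. There the log HR was 1.8% smaller with Breslow, against 0.9% on exact 14-day contacts and 0.25% with ±3-day scatter. A further run gave 0.504 v 0.498 (exact 28-day), 0.501 v 0.498 (exact 14-day), 0.502 v 0.500 (visits clustered on the planned day) and 0.507 v 0.506 (uniform ±3 days).

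**6. Range outside the planning assumptions.** The final sample size is not given.

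- Assumed N = 264, six strata: 0.505 v 0.499 on exact 28-day visits, power 64.3% v 65.6%, verdicts differing in 1.35% of trials. With ±3 days: 0.501 v 0.500, power 66.9% v 67.1%, verdicts differing in 0.2%.
- Assumed 60% placebo relapse: 0.519 v 0.502 on exact visits; 0.501 v 0.498 with ±3 days.

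**7. Under HR = 1.** On exact 28-day visits both methods average 1.00. Rejection in the favourable direction is 2.7% (Breslow) and 3.0% (Efron) against a nominal 2.5%; untied times in the same data give 2.9%. The 6,000-trial run gave 2.3% and 2.5%.

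**The case against.** The strongest reply is that ties will be few and the choice hardly matters. Most of this stands.

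- A reader might infer from SAP section 6.7 that every event time lies on a visit date. The documents do not support that. SAP section 6.6 says "For AEs that meet the primary endpoint criteria, missing or incomplete AE dates are imputed according to BI standards", which would serve no purpose if those relapses took visit dates. The calculations in SAP section 7.4.1 start from the date of the event. Hospitalisation, a medication change or violent behaviour can each have its own calendar date.
- Visits do not sit on an exact grid. "Planned and actual test days will be calculated relative to the beginning of study" in actual days, with ±3-day windows. When worsening is suspected, "an unscheduled in-clinic visit should be scheduled to further assess the patient for relapse". Country strata thin out ties further. Unscheduled visits and separately dated events were not simulated and should reduce ties again.
- A reader might also infer that borderline trials generally lose significance through the tie rule. At the planned size the verdict changes in about 0.1% of trials under the visit windows, and in about 0.9% in the worst case.
- Breslow is an accepted method and, if anything, conservative.

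What remains is that scale-based relapses are recorded at visits under any reading, so some ties will occur. Where the two methods differ, the average effect always goes the same way, and the alternative is one option in the same procedure.

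**Conclusion.** The point holds as a minor improvement. Breslow is fixed in both documents, no analysis varies it, and it pulls the hazard ratio slightly towards 1. At the planning assumptions the shift is about 0.001 to 0.002 with visits spread over the ±3-day window. It is about 0.006 (0.007 from the rounded figures of one run), with less than one point of power, if every relapse fell exactly on a planned 28-day visit. The trial probably lies near the lower end. Larger shifts need conditions the plan does not assume, such as 60% placebo relapse with every event on the exact planned day. At an assumed N = 264 the worst-case power loss is about 1.3 points.

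Type I error is not inflated, and the planned events and sample size stand. The simulations cover only the pooled comparison. The individual-dose tests and time to antipsychotic change share the model, but their shift was not measured, and medication changes may have their own dates and tie less. The result rests on the assumed country shares, constant hazards and visit scatter.

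**What to change.** Before unblinding, replace Breslow with Efron in protocol section 7.3.1 and SAP section 7.4.1 (ties=efron). Apply this to the primary, individual-dose, sensitivity and time-to-antipsychotic-change Cox models. If the primary specification is to stay, pre-specify the Efron fit as a sensitivity analysis; given the size of the effect, that is enough.

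In the same revision, reconcile SAP sections 6.6, 6.7 and 7.4.1 by stating which date each of the six relapse criteria takes, since this determines how many ties there are.

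The cost is one option in the code and a documented SAP change, with no new data. If the treatment codes are already open, the primary method should not be switched, and an Efron fit should be labelled post hoc.
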